14.7	SUSPENSION OR EARLY TERMINATION	26
15	REFERENCES	26

2 Definitions

Term	Definition
Access Circuit	The area from the AV access fistula arterial anastomosis to the axillosubclavian junction.
Access Thrombosis	A total occlusion within the AV access circuit due to thrombus formation which is rapidly evolving as confirmed by sudden onset of symptoms and documented by duplex ultrasound and/or angiography.
Arteriovenous "Dialysis" Fistulae (AVF)	The joining of an artery and vein for the purpose of hemodialysis access.
Clinical Success	Resumption of successful dialysis for at least one session after index procedure.
De Novo Lesion	A lesion that has not been previously treated.
Device Success	Successful delivery, treatment, and retrieval of the FLEX Vessel Prep System or the control device at index procedure.
Dissection Types A-F	
Intimal disruption of the vessel wall with or without medial or adventitial contrast staining, classified as per the NHLBI (National Heart, Lung, and Blood Institute) criteria as follows:
 
A) Luminal Haziness: Minor radiolucent areas in the lumen without impairment of flow or persistent dye staining after contrast runoff.
 
B) Linear Dissection: Luminal flap that is radiolucent and that runs parallel to the vessel wall with contrast injection but without impairment of flow or persistent dye staining after contrast runoff.
 
C) Extraluminal Contrast (i.e., "cap dissection"): Contrast appears outside of the vessel lumen as an "extraluminal cap." The staining appears even after contrast clears the lumen.
 
D) Spiral Dissection: Spiral radiolucent luminal filling defects; often persistent staining after contrast clears from the vessel.
 
E) Dissection with Reduced Flow: New and persistent filling defects in the vessel lumen
 
F) Dissection with Total Occlusion: Lesions that progress to

Term	Definition
	impaired flow or total occlusion
Embolism	The obstruction of a blood vessel by a foreign substance or a blood clot that travels through the bloodstream, lodging in a blood vessel or plugging the vessel.
Enrollment	The time the guidewire has successfully crossed the lesion to be treated.
Optimal PTA	Repeated and prolonged balloon inflations aimed to achieve <50% residual stenosis (visual estimate) without stenting.
Procedural Success	Maintenance of patency ($\leq 30\%$ residual stenosis) in the absence of peri-procedural serious adverse event (SAE) involving the AV access circuit at 30 days post index procedure.
Bail-out Stenting	Placement of a stent due to sub-optimal PTA resulting in either of the following conditions: 
 • Residual stenosis of $\geq 50\%$ (by visual estimate); • Major (\geq Grade D) flow-limiting dissection.
Serious Adverse Event (SAE)	Adverse clinical event where the outcome is: 
 A) Death; B) Life-threatening event (places subject at immediate risk of death from the experience as it occurred); C) Hospitalization (initial or prolonged) if admission to hospital was warranted as a result of an adverse event; D) Disability or permanent damage (substantial disruption of one's ability to carry out normal life functions); E) Congenital anomaly or birth defect; F) Required interventions to prevent permanent impairment or damage; or G) Important medical event that required medical or interventional treatment to prevent one of the previous outcomes, e.g. vascular perforation/rupture, embolism, extravasation, flow-limiting dissection, or hematoma necessitating treatment.
Steal Syndrome* Dialysis-associated steal syndrome (DASS)	Ischemic signs and symptoms (pain, diminished radial pulse, coldness, cyanosis, necrosis) produced by an access device as a result of the diversion of arterial blood flow into the AV fistula.

Term	Definition
Successful Dialysis	
A complete dialysis session includes:
 
 • Normal cannulation and • Is not stopped prematurely.
Target Lesion Re-intervention (TLR)	
Any repeat invasive procedure, including angioplasty, stenting or thrombolysis, performed to open or increase the lumen diameter within the previously treated lesion.
 
Clinically-Driven Target Lesion Re-intervention (CD-TLR): Any re-intervention involving the target lesion in which:
 
 • The subject has a $\geq 50\%$ diameter stenosis in the presence of clinical or physiologic abnormalities that indicate dialysis access dysfunction OR • $\geq 70\%$ stenosis with or without the presence of clinical or physiologic abnormalities indicating dialysis access dysfunction. 
Non-Clinically-Driven Target Lesion Re-intervention: any re-intervention involving the target lesion which does not meet the criteria for CD-TLR.

* Defined by National Kidney Foundation KDOQI Guidelines

3 Protocol Summary

Title	FLEX Vessel Prep prior to PTA for the Treatment of Obstructive Lesions in the Native Arteriovenous Dialysis Fistulae (AVF)
Clinical Study Type	Post Market Outcomes Research Study
Study Device	FLEX Vessel Prep System
Sponsor	VentureMed Group, Inc. [name]
Study Purpose	To evaluate and compare the serious adverse event rate at 30 days and primary patency at 6 months when using FLEX Vessel Prep System prior to PTA vs. PTA alone for treatment of obstructive lesion of native arteriovenous fistulae in the upper extremity.
Primary Efficacy Endpoint	Target Lesion Primary Patency Rate through 6 Months Defined as freedom from clinically driven target lesion re-intervention (CD-TLR) or access circuit thrombosis measured through 6 months post-procedure.
Primary Safety Endpoint	Serious Adverse Event Rate within 30 Days Defined as the Serious Adverse Event (SAE) rate involving the AV access circuit through 30 days post-procedure.
Secondary Endpoints	Secondary endpoints assessed through 6-months: Secondary Safety Endpoint: Serious Adverse Event Rate within 3 and 6 Months Defined as the Serious Adverse Event (SAE) rate involving the AV access circuit through 3 months and 6 months post-procedure. Access Circuit Primary Patency through 3- & 6- Months Post-procedure Defined as freedom from re-intervention in the access circuit or access circuit thrombosis through 3 months and 6 months post-procedure. Target Lesion Primary Patency through 3- & 6- Months Post-procedure Defined as freedom from CD-TLR or access thrombosis occurring in the target lesion through 3 months and 6 months post-procedure. Cumulative Target Lesion Reinterventions (TLR) Measured through 3- & 6- Months Post-procedure Defined as proportion of subjects with TLR through 3 months and 6 months post-procedure.

Secondary Endpoints (Cont.)	
Number of Interventions Required to Maintain Target Lesion Patency through 3- & 6- Months Post-procedure Defined as number of TLR through 3 months and 6 months post-procedure.
 
Number of Interventions Required to Maintain Access Circuit Patency through 3- & 6- Months Post-procedure Defined as number of reinterventions in the target lesion and/or access circuit through 3 months and 6 months post-procedure.
 
Cumulative Access Circuit Thromboses Measured through 3- & 6-Months Post- procedure Defined as proportion of subjects with access circuit thrombosis through 3 months and 6 months post-procedure.
 
Device Success: Defined as successful delivery, treatment, and retrieval of the FLEX Vessel Prep device at index procedure.
 
Procedural Success: Defined as maintenance of patency ($\leq 30\%$ residual stenosis) in the absence of peri-procedural serious adverse event (SAE)
 
Clinical Success: Defined as resumption of successful dialysis for at least one session after index procedure.
 
Balloon opening pressure Defined as minimum inflation pressure required to efface target lesion noting parallel balloon walls.
 
Maximum balloon pressure of angioplasty balloon(s) required during the interventional procedure to treat target lesion.
 
Patient Reported Pain During the interventional procedure reported via Numerical Rating Scale (NRS).

Study Design	A prospective, multi-center, randomized (1:1) clinical study evaluating the FLEX Vessel Prep device plus PTA (study arm) vs PTA alone (control arm) for the treatment of obstructive lesions in the native arteriovenous dialysis fistulae.
Sample Size	Up to 75 Subjects
Number of Sites	Up to 7 clinical sites in the United States.
Study Population	Subjects with a de novo or non-stented restenotic obstructive lesion up to 100 mm in length, located in the native arteriovenous dialysis fistulae in an upper extremity.

Inclusion Criteria	
 1. Patient is ≥ 21 years of age. 2. Patient has a life expectancy of ≥ 12 months. 3. Patient has a native AV fistula created ≥ 60 days prior to the index procedure. 4. The target AV fistula has undergone successful dialysis for at least 8 of 12 sessions during a four-week period. 5. Patient has a de novo and/or non-stented restenotic lesion located between approximately 2 cm proximal to the arteriovenous anastomosis and axillosubclavian junction with $\geq 50\%$ stenosis. 
Note: If the lesion is located in the cephalic arch, the treatment may be delivered up to 2 cm into the subclavian vein.
 
 6. Patient has a target lesion (which may include a tandem lesion) that is ≤ 100 mm in length (by visual estimate). 
Note: Tandem lesions may be enrolled provided they meet all the following criteria:
 
 • Separated from target lesion by a gap of ≤ 30 mm (3 cm). • Total combined lesion length, including 30 mm gap, ≤ 100 mm. • Able to be treated as a single lesion. 
 7. Patient has a target vessel diameter of 4mm – 12mm (by visual assessment). 8. Patient underwent successful crossing of the lesion with the guidewire. 9. Patient provides written informed consent prior to enrollment in the study. 10. Patient is willing to comply with all follow-up evaluations at specified times.
Exclusion Criteria	
 1. Patient is pregnant or breastfeeding. 2. Patient is receiving immunosuppressive therapy. 3. Patient has undergone prior intervention of access site within 30 days of index procedure. 4. Patient with anticipated conversion to peritoneal dialysis. 5. Patient has an infected AV access or systemic infection. 6. Patient has planned surgical revision of access site. 7. Patient with secondary non-target lesion requiring treatment within 30-days post index procedure. 8. Patient with hemodynamically significant central venous stenoses that cannot be successfully treated prior to treatment of the target lesion. 9. Patient with target AVF or access circuit which previously had thrombectomy within last 30 days. 10. Patients judged to have a lesion that prevents complete inflation of an

	
angioplasty balloon or proper placement of the delivery system.
 
 11. Patient with target lesion located central to the axillosubclavian junction. 12. Patient has significant arterial inflow lesion requiring treatment more than 2 cm upstream from the anastomosis in the AV access. 13. Patient has presence of pseudoaneurysm or aneurysm requiring surgical revision at the target lesion site. 14. Patient with known contraindication, including allergic reaction, or sensitivity to contrast material that cannot be adequately pre-treated. 15. Patient who cannot receive recommended antiplatelet and/or anticoagulant therapy. 16. Patient with clinically significant Steal Syndrome requiring treatment. 17. Patient is enrolled in another investigational drug, device, or biologic study and has not completed the primary endpoint or was previously enrolled in this study. 18. Patient has a co-morbid condition that, in the judgment of the Investigator, may cause him/her to be non-compliant with the protocol or confound the data interpretation. 19. Patient has AV fistula created via endovascular technique.
Subject Follow-up	Subjects enrolled in the study will be followed up to 6 months. Follow-up assessments are scheduled for 30-days, 3- & 6-months post index procedure.
Time Course	
Start of enrollment: June 2021.
 
Completed enrollment: April 2022.
 
Planned study close-out: approximately October 2022.

4 Background

In the United States there are approximately 468, 000 patients with end stage renal disease (ESRD) who require routine hemodialysis (HD) as their renal replacement therapy. Among prevalent patients as of December 2018, more than four out of every five patients receiving hemodialysis were using an AV fistula or graft (82.4%; 65.7% fistula and 16.7% graft¹).

The natural history of a hemodialysis access is the persistent development of neointimal hyperplastic stenoses. In fistulas, the most common location of stenoses depends upon the type of fistula. Radial artery-cephalic vein fistulas often develop juxta-anastomotic stenoses, brachial artery to cephalic vein fistulas develop cephalic arch stenoses, often at the site of a hypertrophied valve ring and brachial artery to transposed basilic vein have a predilection to develop stenosis at the swing point of the vein.²

These stenoses cause a reduction in blood flow through the access and thereby decrease the ability to deliver effective hemodialysis treatment. If left untreated, these aggressive lesions will eventually cause the access to thrombose.

Percutaneous transluminal balloon angioplasty (PTA) is the primary technique for treatment of neointimal stenoses associated with prosthetic hemodialysis grafts and native fistulas. It remains the standard treatment to which other percutaneous techniques are compared.

Limitations of PTA include:

- Post angioplasty elastic recoil. After being dilated, elastic elements in the vessel wall cause immediate decrease in lumen diameter.
- Inability to fully dilate a lesion: Dense intimal hyperplasia can be resistant to expansion. Ultra-High-pressure balloons are needed which increase patient discomfort and the risk of vessel rupture.
- Recurrent stenosis.³

Although an angioplasty procedure can provide an excellent immediate result, the long-term patency rates are less than satisfactory with patients requiring an average 1.9 interventions per year.⁴ Clinical studies describing the use of angioplasty to treat hemodialysis fistula-related stenoses have reported six-month patency rates of 25 – 78%.⁵ Angioplasty failures may be due to acute elastic recoil, vascular rupture during balloon inflation or rapid re-growth of the neointimal stenosis. Subsequent dysfunction of the dialysis circuit is a significant cause of morbidity and mortality in patients undergoing HD which results in repeated interventions and can eventually lead to loss of vascular access.

The FLEX Vessel Prep™ system is currently marketed in the United States and cleared via 510K by the Food and Drug Administration (FDA). It is a vessel preparation device indicated for use with percutaneous transluminal angioplasty (PTA) catheters to facilitate dilation of stenoses in the femoral and popliteal arteries and treatment of obstructive lesions of native or synthetic arteriovenous dialysis fistulae. The device is also indicated for treatment of in-stent restenosis of balloon expandable and self-expanding stents in the peripheral vasculature. It is an over-the-wire sheathed system, utilizing a flexible vessel prep treatment element equipped with three flexible struts near the distal tip. The proximal portion of each flexible strut includes a 0.25mm micro-surgical blade. The FLEX Vessel Prep device is placed over an .014" or .018" guidewire distal to the lesion to be treated. The sheath is retracted, and the treatment element is expanded

to contact the lesion. A retrograde pull-back is applied to cross the lesion. The microsurgical blades on the proximal end of each treatment element strut independently engage in the lesion to create three parallel, circumferential continuous micro-incisions, with a depth of approximately 250 microns, along the entire length of the stenosis. The FLEX Vessel Prep treatment element is re-sheathed and advanced again through the lesion to allow a subsequent pullback.

Unlike static PTA balloons, the FLEX Vessel Prep™ System provides continuous engagement of the dynamic treatment element to create micro-incisions along the entire length of the stenosis. Creating longitudinal micro-incisions in the stenosis releases the circumferential tension to enable luminal gain with improved vessel compliance, may reduce the need for high pressure balloons and reduce vessel trauma and complications, including dissection and the need for bail-out stent placement.

Controlled vessel preparation with the FLEX Vessel Prep System may help minimize barotrauma of high-pressure balloon inflation and extend primary patency of the target lesion. Every step that can be taken to improve the outcomes in a patient population that has such limited options, fills a significant unmet clinical need.

5 Objectives and Endpoints

5.1 Primary Objective

To evaluate the 30-day SAE rate and primary patency rates using the FLEX VP System followed by PTA compared with PTA alone for treatment of subjects presenting with obstructive lesions of native arteriovenous dialysis fistulae(AVF) in the upper extremity.

5.2 Endpoints

5.2.1 Primary Endpoints

Primary endpoints for the study are as follows:

- Primary Efficacy Endpoint: Target Lesion Primary Patency Rate through 6 Months

Defined as freedom from clinically driven target lesion re-intervention (CD-TLR) or access circuit thrombosis measured through 6 months post-procedure.

- Primary Safety Endpoint: Serious Adverse Event Rate within 30 Days

Defined as the Serious Adverse Event (SAE) rate involving the AV access circuit through 30 days post-procedure.

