5.2.2 Secondary Endpoints

Secondary endpoints assessed through 6-months (unless noted otherwise) for the study are as follows:

- Secondary Safety Endpoint: Serious Adverse Event Rate within 3 and 6 Months

Defined as the Serious Adverse Event (SAE) rate involving the AV access circuit through 3 months and 6 months post-procedure.

- Access Circuit Primary Patency through 3 Months and 6 Months Post-Procedure
Defined as freedom from re-intervention in the access circuit or access circuit thrombosis through 3 months and 6 months post-procedure.
- Target Lesion Primary Patency through 3 Months and 6 Months Post- Procedure
Defined as freedom from CD-TLR or access thrombosis occurring in the target lesion through 3 months and 6 months post-procedure.
- Cumulative Target Lesion Reinterventions Measured through 3 Months and 6 Months Post-Procedure
Defined as proportion of subjects with TLR through 3 months and 6 months post-procedure.
- Number of Interventions Required to Maintain Target Lesion Patency through 3 Months and 6 Months Post-Procedure
Defined as number of TLR through 3 months and 6 months post-procedure.
- Number of Interventions Required to Maintain Access Circuit Patency through 3 Months and 6 Months Post-Procedure
Defined as number of reinterventions in the target lesion and/or access circuit through 3 months and 6 months post-procedure.
- Cumulative Access Circuit Thromboses Measured through 3 Months and 6 months Post-procedure.
Defined as proportion of subjects with access circuit thrombosis through 3 months and 6 months post-procedure.
- **Device Success:** Defined as successful delivery, treatment, and retrieval of the FLEX Vessel Prep device at index procedure.
- **Procedural Success:** Defined as maintenance of patency ($\leq 30\%$ residual stenosis) in the absence of peri-procedural Serious Adverse Event (SAE).
- **Clinical Success:** Defined as resumption of successful dialysis for at least one session after index procedure.
- **Balloon opening pressure** Defined as minimum inflation pressure required to efface target lesion noting parallel balloon walls.
- **Maximum balloon pressure** of angioplasty balloon(s) required during the interventional procedure to treat target lesion.
- **Patient Reported Pain** During the interventional procedure reported via Numerical Rating Scale (NRS).

6 Study Design

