10.2 Potential Benefits

There are no guaranteed benefits from participation in the study. It is possible that treatment with the FLEX Vessel Prep System prior to use of PTA may improve and maintain blood flow through the treated AVF, resulting in the need for fewer treatments. This may allow for continued/resumption of AV access for the purpose of hemodialysis. Additionally, it is possible that lower balloon inflation pressures following FLEX Vessel Prep use will result in fewer complications and potentially less pain experienced during the procedure. Information gained from the conduct of this study may be of benefit to other persons with the same medical condition.

11 Serious Adverse Event Assessments

The Investigator is required to assess and document in the medical record all Serious Adverse Events (SAEs) observed in subjects from the time of enrollment until the event resolves or the subject exits the study. In cases in which SAEs are unresolved at the time of study exit, this will be documented on the CRF.

The Investigator is responsible for reporting SAEs to VentureMed as soon as possible, but no later than 10 working days after the Principal Investigator is first aware of the event, by completing the Adverse Event CRF. The Principal Investigator is responsible for reporting the SAE to the IRB as applicable.

12 Statistical Design and Methods

This is a prospective, multicenter, randomized (1:1) study of FLEX Vessel Prep prior to PTA vs PTA alone for the treatment of de novo and non-stented restenotic lesions in the AVF. The study will enroll at up to seven centers in the US.

Comparison of binomial proportions will be performed using Fisher's exact test. Time-to-event analyses using the Kaplan-Meier method may be conducted to supplement the primary analysis of proportions. Comparisons of continuous variables will be performed using a two-sample t-test or Wilcoxon rank-sum test.

For the primary efficacy endpoint and other 6-month endpoints that compare the proportion of subjects between arms, the numerator is the number of subjects with an event within 6 months and the denominator is the number of subjects with an event or who were followed for at least 150 days.

For the primary safety endpoint and other 30-day endpoints that compare the proportion of subjects between arms, the numerator is the number of subjects with an event within 30 days and the denominator is the number of subjects with an event or who were followed for at least 23 days.

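### The objective is the 30-day SAE rate and all SAEs are collected, but both labelled safety endpoints count only access-circuit SAEs, and early non-circuit deaths drop out of the analysis

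*Combined protocol and SAP*

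**What the plan says.** **Objective.** Section 5.1 sets out "To evaluate the 30-day SAE rate and primary patency rates" in the two arms. The study purpose in Section 3 likewise speaks of the 30-day SAE rate. Neither attaches a location.

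**Collection.** Under Section 11 the investigator must "document in the medical record all Serious Adverse Events (SAEs) observed in subjects from the time of enrollment". Collection stops at resolution or at study exit. SAEs reach the sponsor on an Adverse Event CRF.

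**Endpoints labelled as safety.** There are two. The primary one (Section 5.2.1) is "Defined as the Serious Adverse Event (SAE) rate involving the AV access circuit through 30 days post-procedure". The secondary one (Section 5.2.2) is "Defined as the Serious Adverse Event (SAE) rate involving the AV access circuit through 3 months and 6 months post-procedure".

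**The limiting term.** Section 2 defines the access circuit as "The area from the AV access fistula arterial anastomosis to the axillosubclavian junction". The protocol does not define *involving*, and it does not say who decides whether an SAE qualifies.

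**Analysis.** For 30-day proportions, Section 12 puts in the denominator subjects who had an event or were followed for at least 23 days. For 6-month proportions the threshold is 150 days. Differences with 95% confidence intervals are promised for all endpoints. The text available describes no all-SAE or death comparison.

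**Procedural Success.** Sections 3 and 5.2.2 require patency "in the absence of peri-procedural Serious Adverse Event (SAE"), with no location attached. Section 2 restricts the same term to SAEs of the access circuit at 30 days.

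**The concern.** The plan states a broad safety question, collects the data to answer it, and then compares a subset. The subset is set by an anatomical term joined to an undefined verb. Some SAEs named in Section 2 need not sit in that stretch of vessel. Death and hospitalization have no anatomical location. Embolism is a listed SAE example, described as material that "travels through the bloodstream, lodging in a blood vessel or plugging the vessel", and nothing confines it to the circuit.

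The denominator rule adds to this. It treats insufficient follow-up as missing data, and death shortens follow-up. An early death that is not counted as a circuit event is therefore handled like a loss to follow-up. A reader could take the result as the SAE rate named in the objective when it leaves out the most serious outcome.

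**Working it through.** **1. The plan's own figure.** Section 12 gives an interval of about ±17% for the safety difference at 5% in both arms. With 75 / 2 = 37.5 per arm, the Wald half-width is 1.96 × √(2 × 0.05 × 0.95 / 37.5) = 1.96 × 0.0503 = 9.9%. At 37 to 37.5 per arm, other methods give 11.5–11.6% (Agresti-Caffo), 12.5–12.6% (Wald with continuity correction), 12.6–12.7% (Newcombe), 14.5% (exact, studentized) and about 22.5–24% (exact, raw difference). None gives 17%. That is a separate matter, and nothing below depends on it.

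**2. Tracing subjects through the rules.** Each row is a hypothetical subject with no other SAE. *Non-circuit* means read by whoever classifies it as not involving the circuit.

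| Event | 30-day numerator | 30-day denominator |
|---|---|---|
| Circuit SAE, day 5 | yes | yes |
| Non-circuit embolism, day 5, subject followed on | no | yes, as event-free |
| Death from a non-circuit SAE, day 10 | no | no |
| Death from a non-circuit SAE, day 25 | no | yes, as event-free |

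The third row follows because the subject has no counted event and 10 days is less than 23. At 6 months the same logic removes a non-circuit death before day 150. Section 12 states no matching rule for 3 months.

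**3. Size of one event.** Expected circuit SAEs at the plan's 5% are 0.05 × 37.5 = 1.9 per arm. One subject is 1 / 37 = 2.7 points, and 2.7 / 5 is about half of the assumed rate.

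**4. Illustration.** Take an arm of 37 with two circuit SAEs, and suppose one further subject dies on day 10 of a non-circuit SAE.

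- Without the death, the circuit endpoint is 2 / 37 = 5.4%.
- With the death, the plan's rule gives 2 / 36 = 5.6%.
- Any SAE over all randomized is 3 / 37 = 8.1%.
- Deaths over all randomized are 1 / 37 = 2.7%.

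The death moves the planned result by about 0.15 points, and only because the denominator shrinks. It moves the any-SAE rate by 2.7 points.

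**5. Precision of the added comparison.** The documents give no all-SAE rate, so this is a range. At an assumed 10% in both arms the Wald half-width at 37.5 per arm is 1.96 × √(2 × 0.10 × 0.90 / 37.5) = 13.6%. At an assumed 15% it is 16.2%. The comparison would be descriptive, as Section 12 already says of the study as a whole.

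**The case against.** A circuit-specific safety endpoint is a declared and legitimate choice for a post-market study of a cleared device. Section 5.1 can be read as shorthand that Section 5.2.1 makes precise. That stands, and the primary endpoint should stay.

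Other harms are not hidden either. SAEs and deaths go to the sponsor, and Procedural Success as worded in Sections 3 and 5.2.2 would turn any peri-procedural SAE into a failure compared by arm. A reader might infer that a non-circuit harm appears in no planned comparison; on that wording, this goes too far. The rescue is uncertain, however, because Section 2 limits Procedural Success to the circuit. Even the broader wording mixes SAEs with residual stenosis, so it yields no SAE rate.

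Four other stronger readings are tempting and are not supported:

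- *Relatedness is never recorded.* The protocol does not ask for relation to device or procedure. The CRF fields are not shown, though, and Section 12 refers to a Statistical Analysis Plan whose separate text is not in the documents.
- *Steal and access sepsis are left out.* Section 2 describes steal as "produced by an access device as a result of the diversion of arterial blood flow into the AV fistula", which can readily be read as involving the circuit, and steal is not among the listed SAE examples. Sepsis arising from the access can be read the same way.
- *Every embolism is left out.* The definition names any blood vessel; it does not say that the embolus lodges outside the circuit.
- *An unblinded site makes the selection.* The site opens the randomization envelope, but nobody is named as classifying SAEs.

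**Conclusion.** The point holds in a limited form. Both labelled safety endpoints are narrower than the stated objective, and the text available plans no comparison of all SAEs or of deaths. An SAE read as outside the circuit is missing from both SAE-rate comparisons. If it is fatal before day 23, the subject is also missing from the 30-day denominator.

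The denominator result follows directly from Section 12, given that the death is not classed as a circuit event. How often that would happen cannot be judged from the documents. The 2.7 points per event is the weight of one subject, not an estimate of bias, and no direction between arms is implied. The conclusion also assumes that material not shown, in particular the separate Statistical Analysis Plan, does not already provide these summaries. If it does, the sponsor need only say so.

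This is a free improvement rather than a flaw that undermines the trial. It lets the study answer its own safety question from data that it already collects.

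**What to change.** Keep the circuit SAE rate as the primary safety endpoint. Add one table by arm, with difference and 95% confidence interval, at 30 days, 3 months and 6 months:

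- (a) subjects with any SAE;
- (b) deaths.

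Use all randomized subjects as the denominator, so that early deaths are not dropped. Subjects who leave early for other reasons then count as event-free after exit, including those withdrawn under Section 9.7 because the access was abandoned. Show their number beside each row.

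Name an interval method that copes with zero counts, such as Newcombe. At an assumed true death rate of 2%, the chance of no deaths among 37 subjects is 0.98^37 = 47%, and a Wald interval has zero width if both arms have none.

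If the CRF already records relation to device or procedure, add related SAEs at any location as a third row. Reconcile the wording of Procedural Success in Section 2 with Sections 3 and 5.2.2. Widening *involving* is not proposed, because it would change the primary endpoint after enrollment was completed (April 2022, Section 3).

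The cost is one table and possibly a higher reported SAE rate. No new data are needed. The table is best specified before results by arm are seen, and otherwise labelled as added afterwards.
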